
2.6 Correlative Studies Background

Nivolumab was initially thought to be most effective in tumors which express PDL1, a marker that may vary in a variety of tumor samples over time, however, with increased experience with this agent, it appears that both PDL1 and nonPDL1 expressing tumors may benefit from nivolumab, either as a single agent or in combination with ipilimumab. Development of biomarkers for response to nivolumab remain under active investigation and are a critical aspect to study design.

We aim to explore the relationship between ORR and PFS to general immune response (CD3, CD4, CD8, FOX-P3, CD68, CD63) as well as more specific markers of immunomodulation including PD-1, PDL-1, PDL-2. We hypothesize that the expression of these markers, either alone or in combination, may lead to the identification of a subset

of patients with ULMS who are more likely to respond to nivolumab. This evaluation will be performed on archival tumor material for all participants when available, and in paired pre/post-treatment biopsies in up to 10 participants. In addition, we have extensive experience using digital scanning of pathology slides and using image analysis to quantify immune infiltrates which will be applied to this cohort and related to response (14). This work will be performed under the direction of [name], PhD and at the Center for Immuno-oncology Pathology Core at Dana Farber–Harvard Cancer Center housed in the Specialized Histopathology Core at the Brigham and Women’s Hospital. The immuno-oncology core at Dana-Farber Harvard Cancer Center (DFHCC) has optimized IHC for these markers (Chen *et al*, 2013) and is actively developing IHC for IDO.

The immuno-oncology core lab at DFHCC evaluation of gene expression profiling with the aim of identification of an immune gene signature with the goal of identify patients more likely to respond to therapy with immune checkpoint inhibitors. Therefore, when material is available, we plan to evaluate targeted expression profiling for immune response signature on FFPE using nanostring platform at the immuno-oncology core at DFHCC (Scott *et al*, 2014).

3. PATIENT SELECTION

3.1 Eligibility Criteria

- 3.1.1 Patients must have histologically or cytologically confirmed advanced leiomyosarcoma of the uterus (ULMS). Advanced ULMS is defined as metastatic ULMS or unresectable primary ULMS.
- 3.1.2 Patients must have measurable disease, defined as at least one lesion that can be accurately measured in at least one dimension (longest diameter to be recorded for non-nodal lesions and short axis for nodal lesions) as ≥ 20 mm (≥ 2 cm) with conventional techniques or as ≥ 10 mm (≥ 1 cm) with spiral CT scan, MRI, or calipers by clinical exam. See Section 11 for the evaluation of measurable disease
- 3.1.3 Patients must have received at least one prior line of chemotherapy, for ULMS (either in the adjuvant or metastatic setting).
- 3.1.4 Age ≥ 18 years. Because no dosing or adverse event data are currently available on the use of nivolumab and ipilimumab in patients <18 years of age, children are excluded from this study, but will be eligible for future pediatric trials.
- 3.1.5 ECOG performance status of 0 or 1 (see Appendix A).
- 3.1.6 Life expectancy of greater than 9 months.
- 3.1.7 Patients must have normal organ and marrow function as defined below:

- absolute neutrophil count $\geq 1,500/\text{mcL}$
- platelets $\geq 100,000/\text{mcL}$
- total bilirubin $\leq 1.5 \times$ institutional upper limit of normal (ULN)
(except patients with Gilbert Syndrome, who can have total bilirubin $< 3.0 \text{ mg/dL}$)
- AST(SGOT)/ALT(SGPT) $\leq 2.5 \times \text{ULN}/\leq 5 \times \text{ULN}$ for subjects with liver metastases
- Serum creatinine $\leq 1.5 \times \text{ULN}$
OR
- creatinine clearance (CrCl) $\geq 50 \text{ mL/min}$ (if using the Cockcroft-Gault formula below):
$$\text{Female CrCl} = \frac{(140 - \text{age in years}) \times \text{weight in kg} \times 0.85}{72 \times \text{serum creatinine in mg/dL}}$$

3.1.8 Patients with a requirement for steroid treatment or other immunosuppressive treatment: Patients should be excluded if they have a condition requiring systemic treatment with either corticosteroids ($> 10 \text{ mg daily prednisone equivalents}$) or other immunosuppressive medications within 14 days of study drug administration. Inhaled or topical steroids and adrenal replacement doses $> 10 \text{ mg daily prednisone equivalents}$ are permitted in the absence of active autoimmune disease.

3.1.9 The effects of nivolumab on the developing human fetus are unknown. For this reason women of child-bearing potential (WOCBP) must agree to use adequate contraception (hormonal or barrier method of birth control; abstinence) prior to study entry and for the duration of study participation. WOCBP should use an adequate method to avoid pregnancy for 31 weeks after the last dose of investigational drug. Women of childbearing potential must have a negative serum or urine pregnancy test (minimum sensitivity 25 IU/L or equivalent units of HCG) within 24 hours prior to the start of nivolumab. Women must not be breastfeeding. Women who are not of childbearing potential (*i.e.*, who are postmenopausal or surgically sterile) do not require contraception.

Women of childbearing potential (WOCBP) is defined as any female who has experienced menarche and who has not undergone surgical sterilization (hysterectomy or bilateral oophorectomy) or who is not postmenopausal. Menopause is defined clinically as 12 months of amenorrhea in a woman over 45 in the absence of other biological or physiological causes. In addition, women under the age of 55 must have a documented serum follicle stimulating hormone (FSH) level less than 40 mIU/mL.

WOCBP receiving nivolumab will be instructed to adhere to contraception for a period of 31 weeks after the last dose of investigational product. These durations have been calculated using the upper limit of the half-life for nivolumab (25 days) and are based on the protocol requirement that WOCBP use contraception for 5 half-lives plus 30 days.

Should a woman become pregnant or suspect she is pregnant while participating in this study, she should inform the treating physician immediately.

The effects of nivolumab on the developing human fetus are unknown.

- 3.1.10 Ability to understand and the willingness to sign a written informed consent document.
- 3.1.11 For enrollment in the first stage of Cohort B, patients must have accessible pre-treatment and post-treatment (4-6 weeks) tumor for biopsy.

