11.1.1 Definitions

Evaluable for toxicity. All patients will be evaluable for toxicity from the time of their first treatment with nivolumab and ipilimumab.

Evaluable for objective response. Only those patients who have measurable disease present at baseline, have received at least one cycle of therapy, and have had their disease re-evaluated will be considered evaluable for response. These patients will have their response classified according to the definitions stated below. (Note: Patients who exhibit objective disease progression prior to the end of cycle 1 will also be considered evaluable.)

Evaluable Non-Target Disease Response. Patients who have lesions present at baseline that are evaluable but do not meet the definitions of measurable disease, have received at least one cycle of therapy, and have had their disease re-evaluated will be considered evaluable for non-target disease. The response assessment is based on the presence, absence, or unequivocal progression of the lesions.

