11.1.2 Disease Parameters

Measurable disease. Measurable lesions are defined as those that can be accurately measured in at least one dimension (longest diameter to be recorded) as ≥ 20 mm (≥ 2 cm) by chest x-ray or as ≥ 10 mm (≥ 1 cm) with CT scan, MRI, or calipers by clinical exam. All tumor measurements must be recorded in millimeters (or decimal fractions of centimeters).

Note: Tumor lesions that are situated in a previously irradiated area will not be

considered measurable, unless there is clear evidence of progression of the lesion since completion of radiation and prior to enrollment on study.

Malignant lymph nodes. To be considered pathologically enlarged and measurable, a lymph node must be ≥ 15 mm (≥ 1.5 cm) in short axis when assessed by CT scan (CT scan slice thickness recommended to be no greater than 5 mm [0.5 cm]). At baseline and in follow-up, only the short axis will be measured and followed.

Non-measurable disease. All other lesions (or sites of disease), including small lesions (longest diameter < 10 mm [< 1 cm] or pathological lymph nodes with ≥ 10 to < 15 mm [≥ 1 to < 1.5 cm] short axis), are considered non-measurable disease. Bone lesions, leptomeningeal disease, ascites, pleural/pericardial effusions, lymphangitis cutis/pulmonitis, inflammatory breast disease, and abdominal masses (not followed by CT or MRI), are considered as non-measurable.

Note: Cystic lesions that meet the criteria for radiographically defined simple cysts should not be considered as malignant lesions (neither measurable nor non-measurable) since they are, by definition, simple cysts.

‘Cystic lesions’ thought to represent cystic metastases can be considered as measurable lesions, if they meet the definition of measurability described above. However, if non-cystic lesions are present in the same patient, these are preferred for selection as target lesions.

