Target lesions. All measurable lesions up to a maximum of 2 lesions per organ and 5 lesions in total, representative of all involved organs, should be identified as **target lesions** and recorded and measured at baseline. Target lesions should be selected on the basis of their size (lesions with the longest diameter), be representative of all involved organs, but in addition should be those that lend themselves to reproducible repeated measurements. It may be the case that, on occasion, the largest lesion does not lend itself to reproducible measurement in which circumstance the next largest lesion which can be measured reproducibly should be selected. A sum of the diameters (longest for non-nodal lesions, short axis for nodal lesions) for all target lesions will be calculated and reported as the baseline sum diameters. If lymph nodes are to be included in the sum, then only the short axis is added into the sum. The baseline sum diameters will be used as reference to further characterize any objective tumor regression in the measurable dimension of the disease.

Non-target lesions. All other lesions (or sites of disease) including any measurable lesions over and above the 5 target lesions should be identified as **non-target lesions** and should also be recorded at baseline. Measurements of these lesions are not required, but the presence, absence, or in rare cases unequivocal progression of each should be noted throughout follow-up.

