11.1.3 Methods for Evaluation of Measurable Disease

All measurements should be taken and recorded in metric notation using a ruler or calipers. All baseline evaluations should be performed as closely as possible to the beginning of treatment and never more than 4 weeks before the beginning of the treatment.

The same method of assessment and the same technique should be used to characterize each identified and reported lesion at baseline and during follow-up. Imaging-based evaluation is preferred to evaluation by clinical examination unless the lesion(s) being followed cannot be imaged but are assessable by clinical exam.

Clinical lesions Clinical lesions will only be considered measurable when they are superficial (*e.g.*, skin nodules and palpable lymph nodes) and ≥ 10 mm (≥ 1 cm) diameter as assessed using calipers (*e.g.*, skin nodules). In the case of skin lesions, documentation by color photography, including a ruler to estimate the size of the lesion, is recommended.

Chest x-ray Lesions on chest x-ray are acceptable as measurable lesions when they are clearly defined and surrounded by aerated lung. However, CT is preferable.

Conventional CT and MRI This guideline has defined measurability of lesions on CT scan based on the assumption that CT slice thickness is 5 mm (0.5 cm) or less. If CT scans have slice thickness greater than 5 mm (0.5 cm), the minimum size for a measurable lesion should be twice the slice thickness. MRI is also acceptable in certain situations (*e.g.* for body scans).

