11.1.4.1 Evaluation of Target Lesions

Complete Response (CR): Disappearance of all target lesions. Any pathological lymph nodes (whether target or non-target) must have reduction in short axis to <10 mm (<1 cm).

Partial Response (PR): At least a 30% decrease in the sum of the diameters of target lesions, taking as reference the baseline sum diameters.

Progressive Disease (PD): At least a 20% increase in the sum of the diameters of target lesions, taking as reference the smallest sum on study (this includes the baseline sum if that is the smallest on study). In addition to the relative increase of 20%, the sum must also demonstrate an absolute increase of at least 5 mm (0.5 cm). (Note: the appearance of one or more new lesions is also considered progressions).

Stable Disease (SD): Neither sufficient shrinkage to qualify for PR nor sufficient increase to qualify for PD, taking as reference the smallest sum diameters while on study.

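### Section 3.1.2 accepts a lymph node of 10 mm short axis on CT as measurable, while Section 11.1.2 requires 15 mm, so a patient can be eligible yet have no target lesion and no route to a partial response

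*Combined protocol and SAP*

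**What the plan says.** **Eligibility.** Section 3.1.2 requires at least one measurable lesion. It says that nodes are recorded by short axis and then gives the same thresholds for nodal and non-nodal lesions: "short axis for nodal lesions) as ≥ 20 mm (≥ 2 cm) with conventional techniques or as ≥ 10 mm (≥ 1 cm", the second figure being for spiral CT, MRI or calipers. The criterion ends with a pointer: "See Section 11 for the evaluation of measurable disease".

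**Measurement.** Section 11.1.2 has a separate rule for nodes: "a lymph node must be ≥ 15 mm (≥ 1.5 cm) in short axis when assessed by CT scan". It places smaller nodes in the other class: "pathological lymph nodes with ≥ 10 to < 15 mm [≥ 1 to < 1.5 cm] short axis), are considered non-measurable disease". Section 5.9 also uses 15 mm short axis for new nodal lesions. Section 11.1.3 takes a different line for superficial lesions measured by hand: "skin nodules and palpable lymph nodes) and ≥ 10 mm (≥ 1 cm) diameter as assessed using calipers".

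**Scoring.** Target lesions are drawn from measurable lesions (11.1.2): "All measurable lesions up to a maximum of 2 lesions per organ and 5 lesions in total". PR is defined on their sum (11.1.4.1): "At least a 30% decrease in the sum of the diameters of target lesions". In 11.1.4.3, the table for patients with non-measurable disease has a CR row but no PR row.

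**Who is counted.** Section 11.1.1 limits evaluability for objective response: "Only those patients who have measurable disease present at baseline". Section 13.6.2 puts all patients who met the eligibility criteria into the main response-rate analysis, with a possible exception only for those who received no study drug.

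**The concern.** The primary endpoint is RECIST 1.1 objective response. The eligibility criterion should therefore admit only patients in whom that endpoint can be scored in full, and the two definitions of a measurable node disagree between 10 and 15 mm. A site that applies 3.1.2 as written can correctly enrol a patient on a 12 mm CT node alone. Section 11 then leaves her without a target lesion.

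Two things are at stake. First, Cohort B continues past stage 1 on a single response among 8 patients, so the scorability of each early patient matters. Second, the same patient is outside the response-evaluable group in 11.1.1 and inside the main analysis in 13.6.2, so two analysts could report different denominators from the same data. Cohort A is closed, so the practical exposure is in Cohort B.

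**Working it through.** **Step 1. Trace one patient through the rules.** Her only lesion is a node of 12 mm short axis on CT.

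| Question | Section | Result |
|---|---|---|
| Meets the eligibility wording? | 3.1.2 | Yes, 12 ≥ 10 mm |
| Measurable? | 11.1.2 | No, 12 < 15 mm |
| Target lesion? | 11.1.2 | None |
| PR possible? | 11.1.4.1, 11.1.4.3 | No |
| CR possible? | 11.1.4.2, 11.1.4.3 | Yes, if the node falls below 10 mm with no new lesions |
| Evaluable for objective response? | 11.1.1 | No |
| In the main response analysis? | 13.6.2 | Yes, if 3.1.2 is taken as met |

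The CR route needs less shrinkage than PR would. For the 12 mm node the margin is (12 − 10)/12 = 16.7%, against 30% for PR. This holds for any sole node below 10/0.7 = 14.3 mm.

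**Step 2. Reproduce the Cohort B design (Section 13.1).** Inputs: 8 + 17 = 25 patients; continue on at least 1 of 8; accept on at least 3 of 25; null 5%, alternative 30%.

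Power = Σ over x ≥ 1 of P(X₁ = x; 8, p) × P(X₂ ≥ max(0, 3 − x); 17, p). At p = 0.30:

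- x = 1: 8 × 0.3 × 0.7⁷ = 0.1977, times P(X₂ ≥ 2) = 0.9807, gives 0.1938
- x = 2: 28 × 0.09 × 0.7⁶ = 0.2965, times P(X₂ ≥ 1) = 0.9977, gives 0.2958
- x ≥ 3: 0.4482, already enough
- Sum: 0.938

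The same formula at p = 0.05 gives a type I error of 0.094. Early stopping under the null is 0.95⁸ = 0.663. The plan states 94%, 9% and 66%, so all three reproduce.

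**Step 3. Upper bound if the conflict stays.** Assume an affected patient has zero chance of response, counts as a failure and is not replaced. One such patient in stage 1 leaves 7 who can respond:

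- False stop at 30%: 0.7⁷ = 0.082, against 0.7⁸ = 0.058
- Power: 7 × 0.3 × 0.7⁶ × 0.9807 + 21 × 0.09 × 0.7⁵ × 0.9977 + 0.3529 = 0.2423 + 0.3169 + 0.3529 = 0.912

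| Affected patients (assumed) | False stop at 30% | Power | Type I error |
|---|---|---|---|
| None | 5.8% | 93.8% | 9.4% |
| One, stage 2 only | 5.8% | 93.6% | 8.8% |
| One, stage 1 | 8.2% | 91.2% | 8.1% |
| Two, stage 1 | 11.8% | 87.6% | 6.8% |

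The counts in the first column are assumptions. The documents give no frequency of disease confined to small nodes.

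**The case against.** **The cross-reference.** Section 3.1.2 points to Section 11, and a careful site following it would not enrol on a 12 mm CT node. This lowers the risk but does not remove it. The criterion states its own number and names nodes, so a reader has no reason to think that number is overridden.

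**CR remains open.** A reader might infer that such a patient is a certain failure in the response analysis. The documents do not support that. Objective response includes CR, 11.1.4.3 allows CR for non-measurable disease, and for most nodes in this range CR needs less shrinkage than PR would. A single confirmed CR of this kind could be the response that opens stage 2. This objection stands in full. The power losses are upper bounds and even the direction of the effect is uncertain.

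**Few patients are exposed.** One other measurable lesion removes the problem. Section 3.1.11 requires biopsy-accessible tumour in stage 1 of Cohort B, which plausibly makes a sole small node less likely there, though it does not exclude one.

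**The denominator is open.** Section 14.1.2 closes accrual once the planned number of evaluable patients has been enrolled, treated and evaluated. That can be read as allowing another patient to be enrolled, in which case the loss could vanish. Section 13.6.2 points the other way. The disagreement is itself part of what needs settling.

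**Section 11 is not uniform.** The 15 mm rule is worded for CT, while 11.1.3 accepts palpable nodes from 10 mm by calipers. The conflict with 3.1.2 is therefore clearest for nodes assessed by CT.

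**Conclusion.** The point holds as an internal contradiction in the current text that bears on the primary endpoint. On CT, 3.1.2 and 11.1.2 disagree for nodes of 10 to under 15 mm. A patient enrolled on such a node alone cannot score PR, and 11.1.1 and 13.6.2 disagree on whether she is counted.

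The size is bounded rather than known. For one affected stage 1 patient the worst case is 2.4 percentage points more false stopping (5.8% to 8.2%, from unrounded values 2.5) and 2.6 points less power (93.8% to 91.2%). For one in stage 2 only, the power loss is 0.2 points. These figures assume that she exists, has no chance of response and is not replaced. The second assumption is stricter than the protocol's own CR rules. It would be wrong to read 91.2% as the trial's actual power, or to conclude that the two-stage design is mis-specified; its stated operating characteristics reproduce. The correction is worth making because the text conflict is clear and the remedy is small.

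**What to change.** 1. In 3.1.2, replace the single 10 mm threshold with the Section 11.1.2 definition: nodes at least 15 mm short axis by CT, and 10 mm for non-nodal lesions.
2. Reconcile the caliper rule for palpable nodes in 11.1.3 with that definition. Changing 3.1.2 alone would leave a second conflict in place.
3. Align 11.1.1 and 13.6.2 on whether an eligible patient without measurable disease is in the response denominator, and make the evaluable-patient wording in 14.1.2 consistent with the answer.
4. If any Cohort B patient has already been enrolled on a node of 10 to under 15 mm alone, report her separately and state how she was counted.

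The cost is a short text amendment. Cohort B stays at 25 patients with the same decision rules, power 93.8%, type I error 9.4% and early stopping under the null 66.3%. The documents give no figure from which to estimate any effect on accrual.

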2. BACKGROUND

2.1 Study Disease – Leiomyosarcoma of the uterus

Sarcomas vary widely in anatomic location as well as histologic subtype, with the current WHO classification listing over 50 distinct histologic subtypes. Prognosis and outcomes can vary widely based on histologic subtype and location of origin; because of this, histology-specific clinical trials in soft tissue sarcomas are necessary to evaluate novel therapies in order to optimize the likelihood of identifying both active and inactive agents within specific sarcoma subtypes.

Uterine sarcomas constitute approximately 3% of all uterine malignancies (Harlow *et al*, 1986). With an estimated incidence of 0.64 cases per 100,000 women, leiomyosarcoma is the most common uterine sarcoma and likely accounts for the single largest site-specific group of leiomyosarcomas (Amant *et al*, 2009). Localized disease is treated with hysterectomy, however rates of local and distant failure are high (45 to 80%), with an

estimated median overall survival of two years once disease is disseminated (Raut *et al*, 2009). Management of metastatic disease focuses on disease control and palliation, often with a combination of systemic therapies and local treatments, surgery and radiation, as indicated. Doxorubicin and gemcitabine based therapies are the most active regimens in this disease with estimated response rates of 20% to 40% with median PFS of approximately 5 -8 months (Omura *et al*, 1993, Look *et al* 2004, Hensley *et al*, 2008)). The most recently FDA approved agent for soft tissue sarcomas, including ULMS, is pazopanib a multi-targeted tyrosine kinase inhibitor. In a phase III placebo controlled trial, pazopanib demonstrated an ORR of 6% and a median PFS of 4.6 months in patients with advanced soft tissue sarcomas who had failed standard prior therapies (van der Graaf *et al*, 2012). Therefore, ULMS remains a disease with a dire need for additional effective systemic therapies.

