 - a: Laboratory testing prior to each dose: Within 72 hrs prior to re-dosing to include CBC w/ differential, LFTs, BUN or serum urea level, creatinine, Ca, Mg, Na, K, Cl, LDH, Glucose, amylase, and lipase. TSH will be collected at screening and repeated every 6 weeks unless clinically indicated. Reflexive Free T4 and Free T3 will be collected at screening and repeated when clinically indicated.
 - b: A serum or urine pregnancy test is required at baseline for women of childbearing potential.
 - c: Off-study evaluation. AE assessment will be performed at 100 days following last dose of study drug. This may be done by phone. Patients who complete all planned protocol therapy (46 doses), will continue to be monitored for tumor measurements beyond completion of treatment until disease progression or the initiation of a new anticancer therapy.
 - d: Pre/post tumor biopsies will be required for all participants.
 - e: Pre-study tumor biopsy to be performed after eligibility is confirmed and patient is registered on study and prior to first dose of combination therapy with nivolumab + ipilimumab .
 - f: Peripheral blood will be drawn prior to study drug infusion for the first 4 cycles to assess changes in immune function as per section 9.2. Samples will also be drawn within 7 days of an objective response, and at off-study.
 - g: Post-treatment biopsy will be performed at approximately week 4-6 (+/- 7 days)
 - h: Archival tissue specimen will be collected if available. This is not required prior to study drug dosing.
 - i: Testing for human immunodeficiency virus (HIV) or known acquired immunodeficiency syndrome (AIDS), hepatitis B virus surface antigen (HBV sAg) and hepatitis C virus ribonucleic acid (HCV antibody) indicating acute or chronic infection. These viral serologies may be performed within 28 days of registration.
 - j: Tumor assessments are repeated every 8 weeks (+/- 2 days) and should continue as per protocol regardless of dosing interruptions.
 - k: For patients with a history of congestive heart failure (CHF) or at risk because of underlying cardiovascular disease or exposure to cardiotoxic drugs, EKG and ECHO will be collected as clinically indicated.
 - l: For patients with evidence of CHF, myocardial infarction (MI), cardiomyopathy, or myositis, cardiac evaluation including lab tests and cardiology consultation (EKG, CPK, troponin levels, ECHO) will be conducted as clinically indicated.

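### The FSH condition in section 3.1.9 runs opposite to a test that confirms menopause, and the definition of childbearing potential contradicts the exemption stated in the same section

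*Combined protocol and SAP*

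**What the plan says.** Section 3.1.9 sets contraception and pregnancy-test requirements for women of childbearing potential (WOCBP). Four of its statements matter here.

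- **WOCBP definition.** It covers any female past menarche "who has not undergone surgical sterilization (hysterectomy or bilateral oophorectomy) or who is not postmenopausal".
- **Menopause definition.** "Menopause is defined clinically as 12 months of amenorrhea in a woman over 45 in the absence of other biological or physiological causes".
- **FSH condition.** The next sentence, introduced as an addition to that definition, says that "women under the age of 55 must have a documented serum follicle stimulating hormone (FSH) level less than 40 mIU/mL".
- **Exemption.** Women not of childbearing potential are glossed as those "who are postmenopausal or surgically sterile) do not require contraception".

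The pregnancy test follows the same classification. Section 3.1.9 says "Women of childbearing potential must have a negative serum or urine pregnancy test", within 24 hours before nivolumab starts. Footnote b of the section 10 calendars says "A serum or urine pregnancy test is required at baseline for women of childbearing potential". No other section gives an FSH threshold, a reference range or a correction.

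**The concern.** The FSH sentence is attached to the clinical definition as a further condition for women under 55, so its evident purpose is to confirm menopause. A confirming test should be passed by women whose ovarian function has ended and failed by those in whom it continues. The stated inequality does the reverse.

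The second problem is internal to the text. The WOCBP definition and the exemption sentence in the same section give different answers for the same woman. Section 2.1 says "Localized disease is treated with hysterectomy", so a premenopausal patient with a prior hysterectomy is a foreseeable case in this trial.

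The classification decides who is tested and who uses contraception before treatment whose fetal effects section 3.1.9 calls unknown. A pre-treatment test that is wrongly omitted cannot be done afterwards. Sites check eligibility before enrolling (section 4.3.2), and two sites reading this paragraph could classify one woman differently.

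**Working it through.** No sample size, power or error rate depends on this point, so the check is a reading of the rules as logic.

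**1. The menopause rule with its FSH condition.** As written, a woman is postmenopausal if:

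age over 45 AND 12 months of amenorrhea without other cause AND (age 55 or over OR FSH below 40 mIU/mL).

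The table applies this to women without surgical sterilization. The FSH values 10 and 80 are illustrations chosen to lie well either side of 40; they are not from the documents. The last column follows the exemption sentence.

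| Woman | Amenorrhea condition | FSH condition | Class as written |
|---|---|---|---|
| Age 50, 12 months of unexplained amenorrhea, FSH 80 | met | failed | WOCBP: test and contraception |
| Age 50, 12 months of unexplained amenorrhea, FSH 10 | met | met | Postmenopausal: neither required |
| Age 50, still menstruating, FSH 10 | failed | met | WOCBP |
| Age 55 or over, 12 months of unexplained amenorrhea | met | not applied | Postmenopausal |
| Age 45 or under, any FSH | cannot be met | irrelevant | WOCBP |

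The FSH condition changes the class only for amenorrheic women aged 46 to 54. In that band it releases the low-FSH woman and retains the high-FSH woman. The third row shows that a low FSH alone reclassifies nobody.

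**2. The WOCBP definition against the exemption.** Let S mean surgically sterilized and P mean postmenopausal. Read literally, the definition makes a woman past menarche WOCBP if (not S) OR (not P). The exemption sentence makes her not WOCBP if S OR P.

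| S | P | Literal definition | Exemption sentence | Agree? |
|---|---|---|---|---|
| yes | yes | not WOCBP | not WOCBP | yes |
| yes | no | WOCBP | exempt | no |
| no | yes | WOCBP | exempt | no |
| no | no | WOCBP | WOCBP | yes |

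They disagree in two of the four cells: the sterilized premenopausal woman and the unsterilized postmenopausal woman.

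**3. The two defects together.** The unsterilized, amenorrheic, low-FSH woman falls in the third row of the second table. The literal definition would keep her as WOCBP; the exemption sentence releases her. Her handling depends on which sentence the site follows.

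**The case against.** The strongest reply is that the defect reaches few patients and that most of its errors are conservative. Much of that stands.

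- **The unsafe group is narrow.** Exposure needs no hysterectomy or bilateral oophorectomy, age 46 to 54, 12 months of amenorrhea without another cause, and FSH below 40, all together. A woman with functioning ovaries and that history would often have another cause and fail the clinical definition first. Every patient has also had chemotherapy (section 3.1.3), itself a possible cause. Cohort A is closed and Cohort B plans at most 25 patients. A reader might infer that premenopausal women in general are released; the amenorrhea condition prevents that.
- **The high-FSH error is cautious.** A reader might infer that menopausal women under 55 are barred from the trial. On the natural reading they are handled as WOCBP, with testing and contraception they may not need.
- **The intent of the or is recoverable.** The exemption sentence treats either route as sufficient. A reader might infer that every premenopausal patient with a hysterectomy is misclassified. That follows only if the exemption is ignored, and the error is toward more testing.
- **Section 3.2.8 excludes pregnant women whatever their label.** That is so, but the required test is limited to WOCBP, so the exclusion does not replace it.

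It can also be said that the documents give no FSH reference range and that the point rests on general physiology. That is correct and is stated as an assumption below. These replies reduce the frequency and consequence of the problem. None supplies a reading under which an FSH below 40 confirms menopause, or under which the two sentences agree as written.

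**Conclusion.** The point holds as a wording defect in a safety-related eligibility rule. The FSH condition for women under 55 runs opposite to a test confirming menopause, and the literal WOCBP definition contradicts the exemption in the same section.

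The number of women exposed in the unsafe direction is not stated and cannot be derived; it is likely to be small. It should be smallest among patients with a prior hysterectomy. The most plausible cases are patients with an unresectable primary tumor, whom section 3.1.1 admits and in whom the uterus may remain.

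The conclusion assumes that FSH rises when ovarian function ends, and that the FSH sentence qualifies the menopause definition it follows. Read instead as a free-standing requirement on all women under 55, it would bar menopausal women with high FSH and demand an FSH value even after hysterectomy, which is no more sensible.

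A reader might infer that the efficacy conclusions are at risk because section 13.6.2 bases them on eligible patients. The documents do not support that: nothing in them links a dispute over childbearing status to removal from the response analysis. The two-stage response-rate design and its operating characteristics are unaffected.

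**What to change.** In section 3.1.9:

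1. Reconcile the FSH sentence with the clinical definition of menopause it is meant to confirm, including the direction of the inequality. The threshold and the clinical rule are for the sponsor to settle; none is proposed here.
2. Reword the WOCBP definition so that surgical sterilization alone, or menopause alone, takes a woman out of the class, as the exemption sentence already says.
3. Carry both corrections into any registration checklist that reproduces the criterion.

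The cost is two wording changes in one eligibility criterion and any matching form. The section already asks for a documented FSH in women under 55, so no test is added, and the sample size does not change.
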